## **7.0 SAFETY VARIABLES AND TOXICITY ASSESSMENT**

### **7.1. Serious Adverse Events**

A ***Serious Adverse Event (SAE)*** is any untoward medical occurrence that at any dose:

- results in death
- is life-threatening (defined as an event in which the participant was at risk of death at the time of the event; it does not refer to an event which hypothetically might have caused death if it were more severe)
- requires inpatient hospitalization or causes prolongation of existing hospitalization (see **NOTE** below)
- results in persistent or significant disability/incapacity
- is a congenital anomaly/birth defect
- is an important medical event (defined as a medical event(s) that may not be immediately life-threatening or result in death or hospitalization but, based upon appropriate medical and scientific judgment, may jeopardize the subject or may require intervention [eg, medical, surgical] to prevent one of the other serious outcomes listed in the definition above.) Examples of such events include, but are not limited to, intensive treatment in an emergency room or at home for allergic bronchospasm; blood dyscrasias or convulsions that do not result in hospitalization.)

- Suspected transmission of an infectious agent (eg, pathogenic or nonpathogenic) via the study drug is an SAE.

Although pregnancy, overdose, potential drug-induced liver injury (DILI), and cancer are not always serious by regulatory definition, these events must be handled as SAEs.

Any component of a study endpoint that is considered related to study therapy should be reported as an SAE (eg, death is an endpoint, if death occurred due to anaphylaxis, anaphylaxis must be reported).

**NOTE:**

The following hospitalizations are not considered SAEs in BMS clinical studies:

- a visit to the emergency room or other hospital department < 24 hours, that does not result in admission (unless considered an important medical or life-threatening event)
- elective surgery, planned prior to signing consent
- admissions as per protocol for a planned medical/surgical procedure
- routine health assessment requiring admission for baseline/trending of health status (eg, routine colonoscopy)
- Medical/surgical admission other than to remedy ill health and planned prior to entry into the study. Appropriate documentation is required in these cases.
- Admission encountered for another life circumstance that carries no bearing on health status and requires no medical/surgical intervention (eg, lack of housing, economic inadequacy, caregiver respite, family circumstances, administrative reason).
- Admission for administration of anticancer therapy in the absence of any other SAEs (applies to oncology protocols)

All Serious Adverse Events (SAEs) that occur following the subject's written consent to participate in the study through 100\* days of discontinuation of dosing must be reported to BMS Worldwide Safety, whether related or not related to study drug. If applicable, SAEs must be collected that relate to any later protocol-specified procedure (eg, a follow-up skin biopsy).

Following the subject's written consent to participate in the study, all SAEs, whether related or not related to study drug, are collected, including those thought to be associated with protocol-specified procedures. The investigator should report any SAE occurring after these aforementioned time periods, which is believed to be related to study drug or protocol-specified procedure.

### 7.1.1 SAE reporting

An SAE report should be completed for any event where doubt exists regarding its seriousness. If the investigator believes that an SAE is not related to study drug, but is potentially related to the conditions of the study (such as withdrawal of previous therapy or a complication of a study procedure), the relationship should be specified in the narrative section of the SAE Report Form. If the BMS safety address is not included in the protocol document (eg, multicenter studies where events are reported centrally), the procedure for safety reporting must be reviewed/approved by the BMS Protocol Manager. Procedures for such reporting must be reviewed and approved by BMS prior to study activation.

An appropriate SAE form (USA = MedWatch form) should be used to report SAEs to BMS. The BMS protocol ID number must be included on whatever form is submitted by the Sponsor/Investigator.

For studies with long-term follow-up periods in which safety data are being reported, include the timing of SAE collection.

The Sponsor will reconcile the clinical database SAE cases (case level only) transmitted to BMS Global Pharmacovigilance ([[contact]](mailto:[contact])). Frequency of reconciliation should be every 3 months and prior to the database lock or final data summary. BMS GPV&E will email, upon request from the Investigator, the GPV&E reconciliation report. Requests for reconciliation should be sent to [[contact]](mailto:[contact]). The data elements listed on the GPV&E reconciliation report will be used for case identification purposes. If the Investigator determines a case was not transmitted to BMS GPV&E, the case should be sent immediately to BMS

The MedWatch form is available at:

<https://www.fda.gov/downloads/AboutFDA/ReportsManualsForms/Forms/UCM048334.pdf>

In accordance with local regulations, BMS will notify investigators of all reported SAEs that are suspected (related to the investigational product) and unexpected (i.e., not previously described in the IB). An event meeting these criteria is termed a Suspected, Unexpected Serious Adverse Reaction (SUSAR). Investigator notification of these events will be in the form of a SUSAR Report.

SAEs, whether related or not related to study drug, and pregnancies must be reported to BMS within 24 hours. SAEs must be recorded on either CIOMS or MedWatch form & pregnancies must be reported on a Pregnancy Surveillance Form or can be submitted on the aforementioned SAE form to BMS.

Other important findings which may be reported by BMS as an Expedited Safety Report (ESR) include: increased frequency of a clinically significant expected SAE, an SAE considered associated with study procedures that could modify the conduct of the study, lack of efficacy that poses significant hazard to study subjects, clinically significant safety finding from a nonclinical (eg, animal) study, important safety recommendations from a study data monitoring committee, or sponsor decision to end or temporarily halt a clinical study for safety reasons.

Upon receiving an ESR from BMS, the investigator must review and retain the ESR with the IB. Where required by local regulations or when there is a central IRB/IEC for the study, the sponsor will submit the ESR to the appropriate IRB/IEC. The investigator and IRB/IEC will determine if the informed consent requires revision. The investigator should also comply with the IRB/IEC procedures for reporting any other safety information.

In addition to the Sponsor Investigator's responsibility to report events to their local HA, suspected serious adverse reactions (whether expected or unexpected) shall be reported by BMS to the relevant competent health authorities in all concerned countries according to local regulations (either as expedited and/or in aggregate reports).

**SAE Email Address:** [contact]

**SAE [contact]

If only limited information is initially available, follow-up reports are required. (Note: Follow-up SAE reports should include the same investigator term(s) initially reported.)

If an ongoing SAE changes in its intensity or relationship to study drug or if new information becomes available, a follow-up SAE report should be sent within 24 hours to BMS (or designee) using the same procedure used for transmitting the initial SAE report.

All SAEs should be followed to resolution or stabilization.

**SAE Reporting for Subsites:** Subsites should report all SAEs to Georgetown using the MedWatch form within 24 hours. Georgetown will then forward SAE reports to BMS Safety within 24 hours through email or fax.

## **7.2. Adverse Events**

An Adverse Event (AE) is defined as any new untoward medical occurrence or worsening of a preexisting medical condition in a clinical investigation participant administered study drug and that does not necessarily have a causal relationship with this treatment. An AE can therefore be any unfavorable and unintended sign (such as an abnormal laboratory finding), symptom, or disease temporally associated with the use of investigational product, whether or not considered related to the investigational product.

The causal relationship to study drug is determined by a physician and should be used to assess all adverse events (AE). The casual relationship can be one of the following:

- a. Related: There is a reasonable causal relationship between study drug administration and the AE.
- b. Not related: There is not a reasonable causal relationship between study drug administration and the AE.

The term "reasonable causal relationship" means there is evidence to suggest a causal relationship.

Adverse events can be spontaneously reported or elicited during open-ended questioning, examination, or evaluation of a subject. (In order to prevent reporting bias, subjects should not be questioned regarding the specific occurrence of one or more AEs.)

#### 7.2.1. Nonserious Adverse Events

Non-serious Adverse Events (AE) are to be provided to BMS in aggregate via interim or final study reports as specified in the agreement or, if a regulatory requirement [eg, IND US trial] as part of an annual reporting requirement.

- Non-serious AE information should also be collected from the start of a placebo lead-in period or other observational period intended to establish a baseline status for the subjects.

A ***non-serious adverse event*** is an AE not classified as serious.

##### 7.2.1.1. Non-serious Adverse Event Collection and Reporting

The collection of non-serious AE information should begin at initiation of study drug. All non-serious adverse events (not only those deemed to be treatment-related) should be collected continuously during the treatment period and for a minimum of 30 days following the last dose of study treatment.

Non-serious AEs should be followed to resolution or stabilization, or reported as SAEs if they become serious. Follow-up is also required for non-serious AEs that cause interruption or discontinuation of study drug and for those present at the end of study treatment as appropriate.

#### 7.3. Adverse Events Associated with the Use of Immune Checkpoint Inhibitor

The immune-related AEs listed below have been reported as related to the use of Nivolumab. Each subject who receives Nivolumab (arms A and C) will be closely monitored by the Investigator and managed, as appropriate, per the respective product labels. In addition, all

immune-related AEs will be evaluated by the Safety Review Committee throughout the conduct of this study.

Subjects in treatment Arms A and C will be monitored for:

- Pneumonitis
- Colitis
- Hepatitis
- Hypophysitis
- Thyroid disorders
- Adrenal insufficiency
- Diabetes mellitus
- Nephritis and renal dysfunction
- Rash
- Encephalitis

#### **7.4. Laboratory Test Abnormalities**

All laboratory test results captured as part of the study should be recorded following institutional procedures. Test results that constitute SAEs should be documented and reported to BMS as such.

The following laboratory abnormalities should be documented and reported appropriately:

- any laboratory test result that is clinically significant or meets the definition of an SAE
- any laboratory abnormality that required the participant to have study drug discontinued or interrupted
- any laboratory abnormality that required the subject to receive specific corrective therapy.

It is expected that wherever possible, the clinical rather than laboratory term would be used by the reporting investigator (eg, anemia versus low hemoglobin value).

##### **7.4.1. Potential Drug Induced Liver Injury (DILI)**

Specific criteria for identifying potential DILI have not been identified for this protocol. Standard medical practice in identifying and monitoring hepatic issues should be followed.

Wherever possible, timely confirmation of initial liver-related laboratory abnormalities should occur prior to the reporting of a potential DILI event. All occurrences of potential DILIs, meeting the defined criteria, must be reported as SAEs.

Potential drug induced liver injury is defined as:

- 1) AT (ALT or AST) elevation > 3 times upper limit of normal (ULN)

**AND**

2) Total bilirubin > 2 times ULN, without initial findings of cholestasis (elevated serum alkaline phosphatase)

**AND**

3) No other immediately apparent possible causes of AT elevation and hyperbilirubinemia, including, but not limited to, viral hepatitis, pre-existing chronic or acute liver disease, or the administration of other drug(s) known to be hepatotoxic.

Wherever possible, timely confirmation of initial liver-related laboratory abnormalities should occur prior to the reporting of a potential DILI event. All occurrences of potential DILIs, meeting the defined criteria, must be reported as SAEs.

**7.5. Pregnancy**

If, following initiation of the investigational product, it is subsequently discovered that a study participant is pregnant or may have been pregnant at the time of investigational product exposure, including during at least 5 half-lives after product administration, the investigational product will be permanently discontinued in an appropriate manner (eg, dose tapering if necessary for participant).

The investigator must immediately notify [[contact]](mailto:[contact]) of this event via either the CIOMS, MedWatch or appropriate Pregnancy Surveillance Form in accordance with SAE reporting procedures. Protocol-required procedures for study discontinuation and follow-up must be performed on the participant. Follow-up information regarding the course of the pregnancy, including perinatal and neonatal outcome and, where applicable, offspring information must be reported on the CIOMS, MedWatch or appropriate Pregnancy Surveillance Form. A BMS Pregnancy Surveillance Form may be provided upon request. Any pregnancy that occurs in a female partner of a male study participant should be reported to BMS. Information on this pregnancy will be collected on the Pregnancy Surveillance Form. In order for Sponsor or designee to collect any pregnancy surveillance information from the female partner, the female partner must sign an informed consent form for disclosure of this information.

**7.6. Overdose**

An overdose is defined as the accidental or intentional administration of any dose of a product that is considered both excessive and medically important. All occurrences of overdose must be reported as an SAE.

**7.7. Other Safety Considerations**

Any significant worsening noted during interim or final physical examinations, electrocardiograms, X-rays, and any other potential safety assessments, whether or not these

procedures are required by the protocol, should also be recorded as a non-serious or serious AE, as appropriate, and reported accordingly.

## **7.8. Study Monitoring**

### **7.8.1 Data Safety Monitoring Committee at Georgetown**

The Georgetown Lombardi Comprehensive Cancer Center (LCCC) will be responsible for the data and safety monitoring of this trial. As this study is an investigator initiated study utilizing FDA-approved on label, and off label therapies, it is considered a high-risk study which requires real-time monitoring by the PI and study team and quarterly reviews by the LCCC Data and Safety Monitoring Committee (DSMC).

The Principal Investigator, [name], and the Study Chair will review the data including safety monitoring at their monthly teleconferences with participating sites.

All SAEs are required to be reported to [name] and the Multicenter Project Manager(s). In additions, SAEs should be reported to the local and/or to the Georgetown IRB per local IRB policy. Based on SAEs, the IRB retains the authority to suspend further accrual pending more detailed reporting and/or modifications to further reduce risk and maximize the safety of participating patients.

Progress on the trial and the toxicities experienced will be reviewed by the LCCC Data and Safety Monitoring Committee every 3 months from the time the first patient is enrolled on the study. Results of the DSMC meetings will be forwarded to the IRB with recommendations regarding need for study closure. DSMC recommendations should be based not only on results for the trial being monitored as well as on data available to the DSMC from other studies. It is the responsibility of the PI to ensure that the DSMC is kept apprised of non-confidential results from related studies that become available. It is the responsibility of the DSMC to determine the extent to which this information is relevant to its decisions related to the specific trial being monitored.

A written copy of the DSMC recommendations will be given to the trial PI and the IRB. If the DSMC recommends a study change for patient safety or efficacy reasons the trial PI must act to implement the change as expeditiously as possible. In the unlikely event that the trial PI does not concur with the DSMC recommendations, then the LCCC Associate Director of Clinical Research must be informed of the reason for the disagreement. The trial PI, DSMC Chair, and the LCCC Associate Director for Clinical Research will be responsible for reaching a mutually acceptable decision about the study and providing details of that decision to the IRB. Confidentiality must be preserved during these discussions. However, in some cases, relevant data may be shared with other selected trial investigators and staff to seek advice to assist in

reaching a mutually acceptable decision. If a recommendation is made to change a trial for reasons other than patient safety or efficacy the DSMC will provide an adequate rationale for its decision. If the DSMC recommends that the trial be closed for any reason, the recommendation will be reviewed by the Associate Director for Clinical Research at LCCC. Authority to close a trial for safety reasons lies with the IRB, with the above described input from DSMC and the Associate Director for Clinical Research.

Of note, the DSMC will also review the safety data of the patients enrolled outside of Georgetown University. The Multicenter Project Manager will be tasked with the job of requesting and collecting primary source documentation for patients enrolled outside of Georgetown University. In addition, the data managers at each site will be entering data into the Georgetown database, so that all data will be available for the DSMC at Georgetown to review. Records should be sent to the Multicenter Project Manager(s) and [name] via email.

## **7.9 Protocol Deviations and Violations**

Protocol deviations (including violations) are cases of drug administration, radiotherapy, clinical laboratory tests, toxicity evaluation, efficacy evaluation, etc., not being carried out in accordance with the study protocol. There are three categories of deviation, as detailed below.

### **7.9.1 Violations**

In general, violations are deviations from the study protocol that meet any one of the following criteria:

1. The deviation affects evaluation of the study endpoints
2. The party responsible for the deviation is a responsible physician and/or medical institution
3. The deviation was deliberate and/or long-term
4. The deviation presented risks for the patients and/or was major
5. As a result of the violation, the procedure followed was inappropriate for clinical use

Violations must be described in detail in all published reports.

### **7.9.2 Deviations**

This refers to deviations that belong to neither the “violation” nor “acceptable deviation” categories. If a particular deviation occurs numerous times, it is preferable for it to be included in published reports.

### **7.8.3. Acceptable Deviations**

Acceptable deviations deviate from the protocol within a range that has been agreed upon, either beforehand or after the fact, by the study group and the Administrative Office.

## **8.0. STATISTICAL CONSIDERATIONS**

### **8.1 Objectives**

### Primary objective:

- 2) To assess the immunologic effects of capecitabine, nivolumab or the combo, post neoadjuvant and post-surgery, in the adjuvant setting, in patients with high risk TNBC as defined by presence of residual disease (breast and or LNs) at surgery, in terms of the change of PIS.
  - a) We hypothesized that among patients with TNBC and residual disease at the time of surgery, the change of the Peripheral ImmunoScore (PIS) from baseline to week 6 will be higher among those who receive post-surgery immunotherapy (ARM A and C), compared to those who receive post-surgery chemotherapy alone (ARM B).

### Secondary objectives:

- 1). To determine the incidence of toxicity graded using the National Cancer Institute CTCAE v. 4.0 until 30 days after last dose of treatment on trial.
- 2). To determine association between changes in PIS from baseline to week 6 and week 12 and clinical outcome variables (DRFS and OS at 2-years). After end of study visit, clinical follow up or telephone communication every 3months.
- 3) To describe the following endpoints and compare them between arms: DRFS, OS
- 4). Translational endpoints:
  - a) To assess changes in
  - b) circulating tumor DNA (ct-DNA) during treatment

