### 2.2 Secondary objectives:

- 1). To determine the incidence of toxicity graded using the National Cancer Institute CTCAE v. 4.0 until 30 days after last dose of treatment on trial.
- 2). To determine association between changes in PIS from baseline to week 6 and week 12 and clinical outcome variables (DRFS and OS at 2-years)). After end of study visit, clinical follow up or telephone communication every 3months.
- 3). To describe the following endpoints and compare them between arms: DRFS, OS
- 4) Translational endpoints:
  - a) Circulating-tumor DNA (ct-DNA)

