## 6.0 STUDY PROCEDURES AND TREATMENT ASSIGNMENT

### 6.1. Table of events

	Pre-registration	Screening	On Study (maximum 6 cycles; cycle is every 21 d)	Treatment discontinuation	Surveillance
	Post-surgery	-30 days	D1 of each cycle +/- 7 days. Each cycle is 21 days.	30 days (+/-7 days) after last dose	
Assessments					
Informed consent	X				
Medical history and height		X			
Physical examination		X	X ^	X	
Weight, BP		X	X ^	X	
ECOG PS		X	X ^	X	
CMP		X	X	X	
Creatinine clearance		X	X	X	
CBC with differential		X	X	X	
Breast imaging (remaining tissue only)					Yearly +/- 30 days
Adverse event and con meds assessment		X	X ^		
Urine pregnancy or serum HCG for WOCBP only		X	X ^ (every 3 weeks) for Arm A and C		
ACTH and Thyroid Function Tests#		X	X ^ (week 12) for Arm A and C	X	
Hepatitis and HIV screening*		X			
EORTC QLQ-C30 &		X	X (week 6)	X	
Telephone communication or focused physical exam+					Every 3-6 months
Treatment					
			Nivolumab 360mg iv q3w; capecitabine 1250mg/m  D1-14		

Correlative Samples					
Tumor from initial diagnosis		X (if available)			
Tumor from definitive surgery – with IHC testing for MSI	X				
Serum for peripheral immunoscore			X ^ (baseline, week 6 and 12)	X (if recurrence)	
Blood for ct-DNA \$			X ^ \$ (baseline, week 6 and 12)	X (if recurrence)	
Tumor from metastatic site				X (if recurrence)	

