### **8.4.2 Secondary Endpoints**

- a. Quantification of immune activation measured by changes of PIS from baseline to week 12 in each arm.
- b. Quantification of grade 3 and 4 toxicities according to the National Cancer Institute Common Toxicity Criteria for Adverse Events Version 4.0 [NCI CTCAE v4.03]
- c. Association between changes in PIS from baseline to week 6 and week 12 and clinical outcome variables (DRFS and OS at 2-years). Distant recurrence free survival (DRFS) is defined by time from study enrollment to date of first invasive distant disease recurrence, second invasive primary cancer (breast or not), or death due to any cause.
- d. To describe the following endpoints and compare them between arms: DRFS, OS
- e. Quantification of ct-DNA at different time points

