### **8.5.2. Analysis for the Secondary Endpoint**

The observed incidence of toxicity will be tabulated according to the grade level and the attribution using the National Cancer Institute CTCAE v. 4.0. Fisher's Exact test will be used to compare the incidence rate of toxicity between treatment groups. We expect that among

patients with TNBC and residual disease at the time of surgery, those who receive post-surgery immunotherapy (ARM A and C) will have longer invasive disease-free survival (DRFS) time compared to those who receive post-surgery chemotherapy alone (ARM B). Patients will be followed for DRFS and overall survival (OS) for 3 years. The Kaplan-Meier method will be used to analyze the DRFS and OS. The DRFS and OS at year 2 will be presented with their 95% confidence intervals. Log-rank test will be used to compare the DRFS and OS between treatment groups.

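### The severe-toxicity endpoint stops at grade 4, so a fatal toxicity falls outside it, and the schedule marks no adverse event assessment at the 30-day visit that closes the toxicity window

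*Combined protocol and SAP*

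**What the plan says.** **The event.** The Synopsis, section 2.2 and section 8.1 give the same toxicity objective: the incidence of toxicity "graded using the National Cancer Institute CTCAE v. 4.0 until 30 days after last dose of treatment on trial". No grade is excluded.

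Section 8.4.2, endpoint b, reads "Quantification of grade 3 and 4 toxicities according to the National Cancer Institute Common Toxicity Criteria". It names grades 3 and 4 only and states no time window.

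Section 8.5.2 then does two things. It describes a table: "The observed incidence of toxicity will be tabulated according to the grade level and the attribution". It also names a test: Fisher's "Exact test will be used to compare the incidence rate of toxicity between treatment groups". The table has no grade cap. The test sentence gives no grade, no attribution and no pair of arms.

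**The schedule.** In section 6.1 the row "Adverse event and con meds assessment" is marked at screening and on study. It is empty in the treatment-discontinuation column, which is headed "30 days (+/-7 days) after last dose". Section 7.2.1.1 says that all non-serious adverse events "should be collected continuously during the treatment period and for a minimum of 30 days following the last dose of study treatment".

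**The concern.** Two parts of the toxicity plan do not line up with the objective they serve.

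First, a severe-toxicity endpoint is normally read as the share of patients with at least one severe event. Here the worst grade is the one left out. A patient with a toxic death and no recorded grade 3 or 4 event would count as having no severe toxicity under endpoint b, so the headline rate would be lowest for exactly the outcome that matters most.

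Second, sites tend to work from the schedule of events. On that table, the visit that closes the analysed window has no entry for adverse event assessment, while the text requires collection up to that point.

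At stake is the accuracy of a secondary safety summary in a 45-patient pilot, and whether its between-arm test is fixed before the data are seen in an open-label trial.

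**Working it through.** The documents give no expected toxicity rate, power or sample size for toxicity, so there is no stated figure to reproduce. The check is a comparison of sections, followed by arithmetic on the schedule and on assumed counts.

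**1. Grades covered, by section**

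| Place | Grades | Grade 5 included? |
|---|---|---|
| Objective (Synopsis, 2.2, 8.1) | no limit | yes |
| Endpoint b (8.4.2) | 3 and 4 | no |
| Table (8.5.2) | by grade, no cap | yes |
| Fisher's test (8.5.2) | not stated | open |

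Only endpoint b excludes a fatal event. The test is compatible with any grade, with grades 3 and 4, or with grade 3 and above.

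**2. Size of one omitted patient.** One patient is 1/15 = 6.7 percentage points of an arm. Sections 4.1.2 and 8.5.1 replace non-evaluable patients, so the treated denominator may be larger: 1/16 = 6.3, 1/18 = 5.6, 1/20 = 5.0 points.

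**3. Illustration for the test (assumed counts; two-sided Fisher p)**

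| Per arm | Events | p | One fewer in the larger count | p |
|---|---|---|---|---|
| 15 | 8 v 1 | 0.014 | 7 v 1 | 0.035 |
| 15 | 7 v 1 | 0.035 | 6 v 1 | 0.080 |
| 15 | 6 v 1 | 0.080 | 5 v 1 | 0.169 |
| 15 | 7 v 2 | 0.109 | 6 v 2 | 0.215 |
| 20 | 7 v 1 | 0.044 | 6 v 1 | 0.092 |

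One patient crosses 0.05 only when the count already sits at the threshold (7 v 1 here). In the other rows the conclusion is unchanged.

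The choice of grades has a similar effect. If nearly every patient has some toxicity, 15/15 v 14/15 gives p = 1.00 and 15/15 v 13/15 gives p = 0.48. The same arms at 7/15 v 1/15 for grade 3 or higher give p = 0.035. The direction is the same in each case; only the significance differs.

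**4. Marks at the 30-day visit (6.1).** Physical examination, weight and blood pressure, ECOG status, CMP, creatinine clearance and CBC are all marked. Adverse event assessment is not. Because the neighbouring rows are filled, a fault in reading the table is unlikely.

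**5. Where the unmarked stretch lies, all cycles on time**

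- Cycle 6 day 1 = 5 × 21 + 1 = day 106. This is the last marked adverse event assessment.
- Arm A: the last dose is on day 106 and the window closes on day 106 + 30 = 136. The stretch after the last mark is 30/136 = 22% of the window.
- Arms B and C: the last capecitabine day is 106 + 13 = 119 (section 5.3) and the window closes on day 119 + 30 = 149. The stretch is 149 − 106 = 43 days, and 43/149 = 29%. It contains 14 of the 6 × 14 = 84 planned capecitabine days.

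The ±7-day visit windows shift these dates. The percentages are shares of the calendar without a mark in the table; they are not shares of events missed.

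**The case against.** The strongest reply on the schedule is that the text closes most of the gap.

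- Section 5.1 requires continuous adverse event monitoring during therapy, which covers cycle 6, and has participants notify their physician of any event.
- Section 7.2.1.1 requires collection for at least 30 days after the last dose.
- Section 6.7 follows continuing events, and section 6.8 covers immune-related events.
- Section 7.1 takes serious events to 100 days.
- Sections 7.4 and 7.7 require significant laboratory results and worsening found on examination to be recorded, and the 30-day visit has both an examination and laboratory tests.

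This stands. A reader might infer from the blank cell that adverse events are not collected after cycle 6 day 1, or that collection then depends on one section alone. The documents do not support either reading. What remains is a table that disagrees with binding text.

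On the endpoint, the reply is that a general objective, a narrower endpoint and an all-grade table can coexist, and that a fatal toxicity would appear in the table, as a serious adverse event, and as a DRFS and OS event. It is right that the death would not be lost, and a reader who infers unrecorded fatal toxicities goes too far. But it would still be missing from the one endpoint meant to count severe toxicity, and nothing in the plan explains that exclusion.

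On the test, the missing grade is underspecification and not a contradiction, and would not justify a point alone. A reader might also infer that the possible definitions give opposite results. The illustrations show a change in significance, not in direction, and the crossing of 0.05 uses counts chosen at the threshold. It also needs a toxic death in a patient with no grade 3 or 4 event, and the documents give no rate for that.

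**Conclusion.** Wrong as written, and minor. Endpoint b excludes grade 5 by its wording, against an objective with no grade limit. Section 6.1 conflicts with section 7.2.1.1 and with the objective's 30-day window. Both follow from the text and need no assumption.

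The practical size is small. The endpoint fault affects only patients whose sole severe toxicity is fatal. For the schedule fault, the number of events missed cannot be derived and could be zero.

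The trial is sized on PIS and accrual feasibility (section 8.2), and no stopping rule or toxicity hypothesis is tied to Fisher's test. Safety oversight runs through quarterly DSMC review and the IRB (section 7.8.1). The p-values above rest entirely on assumed counts and show only why the tested event should be settled before the comparison is run.

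**What to change.** 1. In section 8.4.2, endpoint b, write grade 3 or higher, including grade 5. In section 8.5.2, use the same event, counted once per patient, for Fisher's test. State there whether it is all-cause or treatment-related and which arms are compared; a grade cut-off alone would leave both open. Keep the all-grade table by grade and attribution.
2. Reconcile section 6.1 with section 7.2.1.1 by marking adverse event assessment at the existing treatment-discontinuation visit.

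The cost is a few words in two sections and one table cell, with no added visit. The downside is that the reported severe-toxicity rate may be slightly higher, because fatal events would now be counted.
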